#### **Protocol Synopsis**

**Title:** A Phase 1, First-in-Human, Open-Label Study Evaluating the Safety, Tolerability, Pharmacokinetics, and Efficacy of AMG 562 in Subjects With Relapsed / Refractory Diffuse Large B-cell Lymphoma, Mantle Cell Lymphoma or Follicular Lymphoma

#### Study Phase: 1

**Indication:** Adult subjects with relapsed / refractory Diffuse Large B-cell Lymphoma (DLBCL), Mantle Cell Lymphoma (MCL) or Follicular Lymphoma (FL)

#### Objectives:

#### **Primary Objectives:**

- Evaluate the safety and tolerability of AMG 562 in adult subjects with DLBCL, MCL or FL
- Estimate the maximum tolerated dose (MTD) and/or a biologically active dose (eg, recommended phase 2 dose [RP2D])

#### Secondary Objectives:

- Characterize the pharmacokinetics (PK) of AMG 562
- Evaluate anti-lymphoma activity of AMG 562

#### Exploratory Objectives:

• Evaluate the formation of anti-AMG 562 antibodies

#### Hypothesis:

The maximum tolerated dose (MTD) or recommended phase 2 dose (RP2D) of AMG 562 will have an acceptable safety profile and evidence of anti-lymphoma activity in patients with relapsed and/or refractory B-NHL, specifically DLBCL, MCL or FL as measured by the overall response rate (ORR) and rate of CR.

#### Endpoints:

#### Primary Endpoint:

• Safety: Incidence of dose limiting toxicities (DLTs), treatment-emergent adverse events, treatment-related adverse events, disease-related events and clinically-significant changes in vital signs, physical examinations, electrocardiograms (ECG)s and clinical laboratory tests

#### Secondary Endpoints:

- AMG 562 PK parameters including, but not limited to, maximum concentration (Cmax), minimum concentration (Cmin), time of maximum concentration (Tmax), area under the concentration-time curve (AUC), and if feasible, half-life (t1/2)
- Efficacy parameters:
  - ORR according to Lugano classification

- Overall response by category. [Response terminology reflects the response criteria used. The Lugano Classification response definitions for positron emission tomography-computed tomography (PET-CT) evaluations of fluorodeoxyglucose (FDG)-avid lymphomas uses the terminology complete metabolic response (CMR), partial metabolic response (PMR), no metabolic response (NMR), or progressive metabolic disease (PMD). Corresponding designations from earlier response criteria include complete response (CR), partial response (PR), stable disease (SD), or progressive disease (PD)].
- Duration of response (DOR)
- Progression free survival (PFS)
- Overall survival (OS)

#### **Exploratory Endpoints:**

• Incidence of anti-AMG 562 antibody formation

#### Study Design:

This is a first-in-human (FIH), multicenter, non-randomized, open-label, phase 1 study which will consist of a sequential dose exploration part to evaluate safety and tolerability of AMG 562 in adult subjects with relapsed / refractory DLBCL, MCL, or FL. The dose exploration part will be followed by dose expansion to gain further safety and efficacy with AMG 562 in adult subjects with relapsed / refractory DLBCL. AMG 562 will be administered weekly as an IV infusion with or without a run-in phase (step-up dosing). The run-in phase consists of administration of a low dose on day 1 of treatment and a higher dose (target dose) on day 2. Additional dose steps may be administered subsequently at daily intervals. After administration of the target dose, treatment will continue with weekly administrations of the target dose.

#### **Dose Exploration**

The dose exploration cohorts will estimate the MTD, safety, tolerability, PK, and pharmacodynamics of different doses of AMG 562 in subjects with relapsed / refractory DLBCL, MCL, or FL. Dose exploration will be conducted in 2 stages using a Bayesian logistic regression model (BLRM) design to guide dose escalation. In the initial cohorts, single subjects will be enrolled at dose levels anticipated to be lower than the dose levels at which adverse events related to AMG 562 may be observed. Enrollment will proceed with multiple subject cohorts of 3 to 4 subjects per cohort when higher dose levels are open for enrollment by the Dose Level Review Team (DLRT) or if at least one subject experiences any of the three safety events below (whichever occurs earlier):

- 1. Non hematologic adverse event grade  $\geq 2$
- 2. Hematologic adverse event grade ≥ 3 including anemia, neutropenia, leukopenia, thrombocytopenia, and lymphopenia
- 3. DLT

AMG 562 will be administered as IV infusions at weekly intervals. If no DLTs are observed, the dose escalation will continue to the next planned dose cohort as shown Table 1 below. Once a

subject experiences a DLT, the dose for the subsequent cohorts will be recommended by the DLRT after evaluating all available safety, laboratory, and PK data as well as the recommendation from the BLRM. Subsequent dose escalation will be limited to 2-fold increases or lower after a subject experiences a DLT or  $\geq 2$  patients experience a grade  $\geq 2$  adverse event.

Cohort	Dose (µg)	Cohort Size
1	0.1	1
2	0.3	1

Table 1. Planned Dose Levels (IV)

The DLRT may also recommend altering the dosing schedule (dosing interval) for subsequent cohorts. The changes to the dosing schedule may also include the implementation of step-up dosing for future cohorts based on tolerability as observed in the clinical and pharmacological data.

The DLT evaluation period will be at least 28 days for all cohorts. The DLT evaluation period may also be extended to assess events starting within the DLT window. Any adverse event occurring outside the DLT window that meets the DLT definition and is determined by the investigator to be possibly related to AMG 562, and seen more frequently, or is more severe than expected, or is persistent despite appropriate management, can be determined to be a DLT upon unanimous decision by the DLRT after review of the event and all available safety data. A DLRM will be conducted after the subjects in each dose cohort have had the opportunity to complete the DLT evaluation period. The DLRT may also convene at any time to review safety data if deemed necessary.

Subjects who complete the DLT period may proceed to a higher dose level for the next dosing (intra-subject dose escalation) once this higher dose level has been deemed safe by the DLRT and after consultation with the Amgen Medical Monitor if:

- no DLT has been reported for this subject during or after completion of the DLT period
- the subject has not experienced any grade ≥ 2 adverse events (deemed treatment related by the investigator) during treatment

DLTs experienced by subjects after completing the DLT period will be considered in the BLRM design to account for any late onset toxicity.

Dose exploration will continue until any of the following events:

The highest planned dose level is determined to be safe and tolerable (minimum of 6 treated subjects)

- An MTD is identified where BLRM repeats the recommendation of a dose level (minimum of 6 treated subjects)
- If fewer than 6 subjects are treated at the MTD/RP2D, additional subjects may be enrolled to confirm safety and tolerability.

#### **Dose Expansion**

At completion of the dose exploration cohorts, additional subjects (up to 55) will be enrolled in a dose expansion cohort to gain further clinical experience, safety and efficacy data for AMG 562 in subjects with relapsed / refractory DLBCL. The dose to be evaluated will be at or below the MTD estimated in the dose exploration cohorts. Additional expansion cohorts may be covered by a protocol amendment to test alternative dose levels or biologic subsets or other disease entities included in the dose exploration. A final estimate of the MTD and RP2D will be evaluated and confirmed utilizing all DLT-evaluable subjects from the dose exploration and the dose expansion cohorts. The clinical activity of AMG 562 in the expansion cohort will be examined using a Bayesian predictive probability design. If posterior probability is more than 85% that the ORR is 40% or less then, this is considered insufficient anti-lymphoma activity. The guidelines for futility due to insufficient efficacy assuming a prior beta distribution (0.8, 1.2) are presented in Table 2.

Number of Treated Subjects	Efficacy Futility Guideline
15	4 or fewer responders
20	5 or fewer responders
25	7 or fewer responders
30	9 or fewer responders
35	11 or fewer responders
40	12 or fewer responders
45	14 or fewer responders
50	16 or fewer responders
55	Trial will stop

 Table 2. Futility Guidelines

The DLRT will be convened in the dose expansion part of the study to review efficacy data after the first 15 subjects are enrolled and have had the opportunity to receive at least five weeks of treatment (with recruitment ongoing).

Additionally, the DLRT will review safety data and conduct evaluations of the ongoing DLT rate to assess if the threshold for early trial termination has been reached. The stopping rules use a Bayesian approach to terminate the study if the posterior probability that the DLT rate is greater than 33% is > 90%. The stopping boundaries assuming a prior beta distribution (0.66, 1.33) are presented in Table 17. The evaluations could occur more frequently if necessary to address emerging safety concerns

#### Sample Size:

It is anticipated that approximately 85 subjects will be enrolled in this study. Approximately 30 subjects will be enrolled in the dose escalation cohorts and up to 55 additional subjects will be enrolled in the dose expansion cohort. The sample size in the dose escalation is based on

practical considerations and is consistent with conventional oncology studies with the objective to estimate the MTD. With 3 subjects per cohort, there is a 27-70% probability of observing at least one DLT if the true DLT rate is 10-33% and with 4 subjects per cohort, there is a 34-80% probability. In the dose expansion cohort, 55 subjects will provide a 43% probability of observing at least one adverse event with a true 1% incidence rate and 94% probability of observing at least one adverse event with a true 5% incidence rate. With 55 subjects and a 40% overall response rate, the expected 90% CI would be 29% to 52%.

#### Summary of Subject Eligibility Criteria:

Male or female subjects  $\geq$  18 year of age at the time of informed consent who have

• Relapsed / refractory DLBCL after appropriate prior treatment, with relapse after at least 2 lines of therapy, with one or more regimens including an anthracycline AND an approved anti-CD20 agent

or

 Relapsed / refractory FL after appropriate prior treatment, with relapse after at least 3 lines of therapy, with at least one or more regimens including an approved anti-CD20 agent

or

 Relapsed / refractory MCL after appropriate prior treatment, with relapse after at least 3 lines of therapy, with at least one or more regimens including an approved anti-CD20 agent

at time of screening. The diagnosis must be biopsy proven and subjects must have measurable disease at screening as defined in the inclusion criteria. Subjects who received prior CD19 directed CAR-T cell therapy are excluded.

#### **Investigational Product**

Amgen Investigational Product Dosage and Administration:

AMG 562 will be manufactured and packaged by Amgen Inc. and distributed using Amgen clinical study drug distribution procedures.

AMG 562 is supplied as a sterile, preservative-free lyophilized powder for IV administration after reconstitution with sterile water for injection (WFI).

AMG 562 solution for infusion will be prepared in bags for IV infusion and delivered through infusion lines. The Investigational Product Instruction Manual (IPIM), a document external to this protocol, contains detailed information regarding the storage, preparation, destruction, and administration of AMG 562.

The initial duration of infusion will be **a second second** 

- Minimum hospitalization times for subjects will be as follows:
- Without step-up dosing:
  - 72 hours after infusion at C1D1 and C1D8
  - 48 hours after infusion at C1D15 and C1D22 if there are no adverse events ≥ grade 1 up to day 15, otherwise 72 hours.
  - For all subsequent infusions subjects should be monitored in hospital or outpatient clinic for at least 4 hours after start of each infusion with hospitalization at the discretion of the investigator

- 72 hours after infusion at day 1, after every step dose infusion and for the first two infusions at target dose (similar to C1D1 and C1D8 without step-dosing)
- 48 hours after the 3rd and 4th infusion at target dose if there are no adverse events ≥ grade 1, otherwise 72 hours.
- For all subsequent infusions, subjects should be monitored in hospital or outpatient clinic for at least 4 hours after start of each infusion with hospitalization at the discretion of the investigator

The DLRT may recommend on changes in hospitalization requirements after review of available safety data.

Treatment can be administered as long as the subject is deriving benefit per the judgment of the investigator, unless one of the criteria for permanent discontinuation of treatment is met. Treatment can be discontinued 4 weeks after a CR/CMR is confirmed by the investigator after consultation with the Amgen Medical Monitor.

**Procedures**: After providing informed consent, eligible subjects will undergo the following assessments during this study: physical examination, neurological examination, Eastern Cooperative Oncology Group (ECOG) status, height, weight, vital signs, pulse oximetry, ECG triplicate measurement, laboratory assessments (including serum pregnancy test, if applicable, coagulation, hematology, blood chemistry profiles, urinalysis, hepatitis serology, and anti-AMG 562 antibody test), biomarker and PK assessments, immunoglobulin levels (IgG, IgA, IgM), PET-CT (per standard of care), and bone marrow biopsy (per standard of care). Reporting of adverse events, disease related events, and cases of pregnancy and lactation will be performed as described in the study procedures.

**Statistical Considerations:** The primary analysis for the dose exploration part will occur when targeted enrollment is complete and each subject either completes 3 months on study or is taken off from the study by the Investigator. The primary analysis for the dose expansion part will occur when targeted enrollment is complete and each subject had the opportunity to receive at least 3 months of treatment at the target dose.

In the dose exploration part, the DLRT will review the safety data after each cohort and make a recommendation on the next dose level to be explored for the estimate of RP2D/MTD based on a BLRM design. In the dose expansion part, efficacy futility and safety will be assessed using a Bayesian predictive probability design.

Descriptive statistics will be provided for selected demographics, safety, PK, pharmacodynamic, efficacy and biomarker data by dose, dose schedule, and time as appropriate. Descriptive statistics on continuous data will include means, medians, standard deviations and ranges, while categorical data will be summarized using frequency counts and percentages. ORR will be presented with 90% exact CI. PFS will be summarized using the Kaplan-Meier method. Graphical summaries of the data may also be presented.

For a full description of statistical methods, please refer to Section 10.

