#### Without step-up dosing:

- 72 hours after infusion at C1D1 and C1D8
- 48 hours after infusion at C1D15 and C1D22 if there are no adverse events grade ≥1 up to day 15, otherwise 72 hours.
- For all subsequent infusions subjects should be monitored in hospital or outpatient clinic for at least 4 hours after start of each infusion with hospitalization at the discretion of the investigator

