#### With step-up dosing:

- 72 hours after infusion at day 1, after every step dose infusion and for the first two infusions at target dose (similar to C1D1 and C1D8 without step-dosing)
- 48 hours after the 3rd and 4th infusion at target dose if there are no adverse events grade ≥ 1, otherwise 72 hours.
- For all subsequent infusions, subjects should be monitored in hospital or outpatient clinic for at least 4 hours after start of each infusion with hospitalization at the discretion of the investigator

In case of intra-subject dose escalation, subjects will be hospitalized as per the guidance for treatment initiation.

The DLRT may recommend changes in hospitalization requirements after review of available safety data. The hospitalization period for individual subjects may be extended at the discretion of the investigator. Any shortening of hospitalization period can only be implemented with the official approval of a substantial amendment of the protocol.

Study sites must have immediate access to a medical intensive care unit staffed by critical care providers. Prior to hospital discharge, vital signs will be measured in order to detect possible signs and symptoms of infusion reactions or CRS. If required for

logistical reasons (eg, long travel times), subjects may be hospitalized the day before start of dosing, as well as during the treatment period for required PK samples.

The start time of infusion should be chosen carefully so as to avoid any interference or inconvenience with time points of safety assessments or PK/pharmacodynamic measurements.

The planned dose, quantity administered (amount and concentration), start date/time, stop date/time, and lot number of investigational product are to be recorded on each subject's electronic case report form (eCRF).

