#### 6.2.1.4.2.4 Re-Start of Infusion

Re-starting treatment after an interruption/delay due to an adverse event or if the interruption/ delay was > 72 hours, regardless of the reason, should be performed under medical supervision. Premedication as described in Section 6.3 for the first infusion of the treatment should be considered prior to re-start. The following assessments should be performed as for Days 1, 2, and 3 of the treatment (see Schedule of Assessments, Table 8):

- vital signs, pulse oximetry,
- physical examination (including neurological examination, if applicable)
- weight

CONFIDENTIAL

- ECOG
- safety Labs (hematology, chemistry, coagulation, urinalysis)

The subject should be hospitalized for at least 48 hours after re-start of the infusion.

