#### 6.2.1.4.2.6 Specific Guidance for Cytokine Release Syndrome

Cytokine release syndrome is clinically defined and may have various manifestations.

There are no established diagnostic criteria. Signs and symptoms of CRS may include:

• constitutional: fever, rigors, fatigue, malaise

- neurologic: headache, mental status changes, dysphasia, tremors, dysmetria, gait abnormalities, seizure
- respiratory: dyspnea, tachypnea, hypoxemia
- cardiovascular: tachycardia, hypotension
- gastrointestinal: nausea, vomiting, transaminitis, hyperbilirubinemia
- hematology: bleeding, hypofibrinogenemia, elevated D-dimer
- skin: rash

Subjects may be at an increased risk for CRS during the first few days following the infusion of AMG 562. CRS may be life threatening or fatal. Infusion reactions may be clinically indistinguishable from manifestations of CRS. Throughout the treatment with AMG 562, monitor subjects for clinical signs (eg, fever, tachycardia, dyspnea, tremors) and laboratory changes (eg, transaminase increase) which may be related to CRS.

Grading and management of CRS should be performed according to the guidelines provided in Table 7 (based on the adopted grading system referenced in Lee et al, 2014).

After grade 2 or 3 CRS, the next scheduled infusion may be administered if all of the following criteria are met:

- The Amgen Medical Monitor must be consulted prior to re-starting treatment
- If CRS occurred during AMG 562 infusion, infusion has been interrupted for at least 72 hours

The event has resolved to grade  $\leq$  1 prior to re-starting treatment

Please also refer to the general guidance for re-start of infusion after interruptions/delay/withholding and dose modifications in Section 6.2.1.4.2.

For grade 3 and 4 CRS, please also see Section 6.2.1.3 for DLT considerations.

CRS Grade	Description of Severity a	Interruption/ Delay/ Withholding	Minimum Expected Intervention	Restart Guidance	Permanent Discontinuation
2	Symptoms are not life threatening and require symptomatic treatment only, eg, fever, nausea, fatigue, headache, myalgias, malaise	n/a Immediately	Administer symptomatic treatment (eg, paracetamol/ acetaminophen for fever). Monitor for CRS symptoms including vital signs and pulse oximetry at least Q2 hours for 12 hours or until resolution, whichever is later. Administer:	n/a	n/a If there is no

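### Without step-up dosing, the C1D22 minimum stay ignores adverse events after day 15, so a first event on days 16–21 still gives only 48 hours

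*Protocol*

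**What the plan says.** Section 6.2.1.1 of the protocol sets minimum hospital stays. Without step-up dosing these are 72 hours after C1D1 and after C1D8, and then "48 hours after infusion at C1D15 and C1D22 if there are no adverse events grade ≥1 up to day 15, otherwise 72 hours". The Synopsis gives the same rule: "48 hours after infusion at C1D15 and C1D22 if there are no adverse events ≥ grade 1 up to day 15, otherwise 72 hours". One condition, with one cut-off day, therefore governs two infusions that are a week apart.

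The step-up counterpart covers the third and fourth target-dose infusions: 48 hours after each "infusion at target dose if there are no adverse events grade ≥ 1, otherwise 72 hours". It has no day-15 cut-off, although it states no look-back period either.

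The same section adds two qualifications. Stays can be lengthened case by case: "The hospitalization period for individual subjects may be extended at the discretion of the investigator". Reductions are restricted: "Any shortening of hospitalization period can only be implemented with the official approval of a substantial amendment of the protocol".

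Other parts of the protocol also set stays. After an interruption or delay for an adverse event, Section 6.2.1.4.2.4 says "The subject should be hospitalized for at least 48 hours after re-start of the infusion". Table 7 gives 48 hours on re-start after grade 2 CRS. Table 6 gives 72 hours on re-start after a grade 3 CNS event.

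**The concern.** For C1D15 the cut-off coincides with the infusion. For C1D22 it is seven days old. Anything that first appears on days 16–21, which is the reaction period of the third dose, cannot lengthen the stay after the fourth. An event on day 3 that has long since resolved does lengthen it. The more recent signal gets less observation.

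The protocol itself explains why those hours matter. In Section 6.2.1.4.2.6 it says "Subjects may be at an increased risk for CRS during the first few days following the infusion of AMG 562" and warns that CRS can be fatal. Table 4 lists hospitalization among the CRS safety measures. The 72-hour tier is for subjects who have shown an event, and in this first-in-human study the rule withholds it at C1D22 from those whose first event followed the latest dose. The documents give no reason for fixing the C1D22 cut-off at day 15.

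**Working it through.** **Step 1. Apply the rule to the two cases.**

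- Case A: no event through day 15, first grade 1–2 event on days 16–21, C1D22 given. The condition is met, so the C1D22 minimum is 48 h.
- Case B: grade 1 event on day 3, resolved. The condition fails, so the minimum is 72 h at both C1D15 and C1D22.

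**Step 2. Look for a mandatory rule that overrides Case A.**

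- Grade 1 CRS (Table 7): described as "Symptoms are not life threatening and require symptomatic treatment only, eg, fever, nausea, fatigue, headache, myalgias, malaise". There is monitoring, but no delay, re-start or hospitalization rule.
- Grade 2 CRS (Table 7): 48 h.
- Grade 2 infusion reaction (Table 6): refers to Section 6.2.1.4.2.4, which requires at least 48 h.
- CNS grade 3 (Table 6): 72 h, but outside the grade 1–2 range. A grade 2 seizure is an edge case. The 7-day hold would delay or skip the day 22 dose, and the 72-hour sentence in Section 6.2.1.4.3 might be read to cover it.
- Grade 3 CRS has its own hospitalization rule, and grade 4 CRS means permanent discontinuation.
- Appendix I has a 72-hour PK draw on day 25, which does not require an inpatient stay.
- The Table 8 grid was not legible in the text available, but its hospitalization footnote refers back to Section 6.2.1.1.

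Nothing generally requires hours 48–72 in Case A.

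**Step 3. Minimum cycle 1 hospital hours (C1D1 + C1D8 + C1D15 + C1D22), as written and with the change proposed below.** *Up to day 15* is read as including the whole of day 15.

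| First event of grade 1 or higher | As written | With the change |
|---|---|---|
| None | 72+72+48+48 = 240 | 72+72+48+48 = 240 |
| Days 1–15 | 72+72+72+72 = 288 | 72+72+72+72 = 288 |
| Days 16–22 | 72+72+48+48 = 240 | 72+72+48+72 = 264 |

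**Step 4. How many subjects?** The documents give no event rate. As an illustration, assume a constant daily rate of first event and let p be the share event-free through day 15. The share event-free through day 21 is then p^(21/15) = p^1.4, and the share with a first event on days 16–21 is p − p^1.4.

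- p = 0.05: 0.05 − 0.015 = 0.035
- p = 0.10: 0.10 − 0.040 = 0.060
- p = 0.50: 0.50 − 0.379 = 0.121
- Maximum: setting 1 = 1.4·p^0.4 gives p = 0.43 and a share of 0.123

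The trigger is any adverse event, related or not (Section 9.1.2), so few subjects are likely to be event-free through day 15. The lower figures are therefore the more plausible ones.

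**The case against.** **It may be deliberate.** The stays are stated as minimums, and they step down from 72 to 48 hours once a subject has come through the first infusions without any event. Section 3.1 names first-dose effects as the concern, so basing the step-down on early exposure would be coherent. However, that text introduces step-up dosing and does not explain this rule. The step-up rule itself has no day-15 cut-off.

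**Other protections exist.**
- Toxicity is assessed before each infusion.
- Dexamethasone precedes every cycle 1 dose.
- Grade 2 CRS requires resolution to grade 1 or lower, Medical Monitor consultation and a dose reduction before re-start.
- Section 6.2.1.4.2.4 repeats the safety assessments after an AE-related delay.
- Grade 2 or higher neurotoxicity brings daily extended neurological examination.
- The DLRT can recommend changes to hospitalization, and the investigator can extend a stay.

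These make the next dose after several grade 2 events a managed one, and the gap bears mainly on grade 1 events. They reduce the risk, but none mandates hours 48–72.

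**The overlap between rules is mostly reconcilable.** A 72-hour stay satisfies both Section 6.2.1.1 and the at-least-48-hours re-start rule. Only Table 7's entry for grade 2 CRS, a bare 48 hours, leaves doubt. An event on days 1–15 gives 72 hours under Section 6.2.1.1 and 48 under Table 7. This is a secondary point.

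**The illustration is generous.** If risk is concentrated after the first dose, the share with a first event on days 16–21 is lower than a constant rate suggests. That is right.

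**It is largely past.** The SAP (Sections 1 and 7.2) reports early discontinuation with one ongoing subject, and the documents do not say that subject is in cycle 1. This limits the practical effect but does not make the wording right.

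**Conclusion.** The concern holds as a minor point. Read literally, the rule gives a longer C1D22 stay for an old, resolved event than for a first event after the latest infusion, and no mandatory provision generally corrects this for grade 1–2 events. The size is 24 hours at one infusion. The affected share is unknown. It is at most about 12% under the constant-rate assumption and probably well below that. The 288-hour figure for a first event on day 15 after dosing assumes that the whole of that day counts, which the text does not spell out. No endpoint, estimate or stopping rule is affected, and little further cycle 1 use of the rule is expected. The correction is worth making if the protocol is amended or the clause is reused elsewhere.

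**What to change.** In the Synopsis and in Section 6.2.1.1, for dosing without step-up, replace *up to day 15* with *up to and including the day of that infusion*. The C1D15 stay then depends on events through day 15 and the C1D22 stay on events through day 22. Add one sentence: where Table 6, Table 7 or Section 6.2.1.4.2.4 gives a different minimum, the longer stay applies.

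Do not use *before that infusion*. A first event on day 15 after dosing would then no longer give 72 hours at C1D15, and the cycle 1 minimum would fall from 288 h to 72+72+48+72 = 264 h. That is a shortening, which Section 6.2.1.1 allows only by substantial amendment.

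The cost is one phrase in two places, one added sentence, and one extra night at C1D22 for flat-dosed subjects whose first event falls on days 16–22. Under the same constant-rate assumption, that share is p − p^(22/15), with a maximum of 14.0%. No stay set by the current rule becomes shorter.
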